Form "EAST Multicenter Study Proposal"

Details #22 (submitted 09/29/2023)

Please indicate if this is

a...

New MCT proposal submission

If a revised proposal summarize the changes made to this proposal based on the feedback received:

Study Title

Standard Thromboelastography Protocols May Fail to Identify Coagulopathy in Hypothermic Trauma Patients – An EAST Multicenter Study

Primary Investigator:

[name]

Institution that will be the primary site for the study:

University of Arkansas for Medical Sciences

Email of Primary Investigator:

[contact]

Co-PI/second point of contact for the study:

[name]

Email of Co-PI/second point of contact for the study:

[contact]

Are you a current member of EAST?

Yes

If you selected "No" above please identify a Sponsor that is an active EAST member:

Background: Trauma remains the leading cause of death in individuals younger than 40, with hemorrhage being the primary preventable cause.¹⁻⁴ Hemorrhage from trauma is frequently exacerbated by coagulopathy, which is a multifactorial process that can have devastating consequences irrespective of injury severity. Hypothermia is also a known component of the lethal triad and can worsen coagulopathy, and is highly pertinent to the trauma population as an estimated >20% of trauma patients will be hypothermic on arrival to treatment center.⁵ Extensive research has focused on optimal resuscitative strategies in patients with trauma-induced coagulopathy (TIC); however, the impact of hypothermia on the viscoelastic properties of blood clots remain unknown.⁶⁻⁸

Massive transfusion protocols and blood management programs must balance the risk of unnecessary exposure to blood products with the need for adequate treatment of severe bleeding. As a result, Rotational Thromboelastometry (ROTEM) and Thromboelastography (TEG) are commonly used blood tests that evaluate the viscoelastic properties of blood clot formation. ROTEM or TEG are utilized, depending on institutional preferences, in bleeding trauma patients to guide appropriate utilization of blood products and reverse coagulopathy.⁹⁻¹² The impact of hypothermia on ROTEM samples remains unknown, with current literature on hypothermic viscoelastic properties being conducted utilizing TEG in animal studies or healthy volunteers.

Use this area to briefly outline the burden of the problem to be examined.

Significance: Given the frequent utilization of viscoelastic testing and the critical condition of the patients for whom ROTEM or TEG is intended, comprehending mechanical aspects of these tests is important. As previously indicated, bleeding trauma patients confront a multifaceted ailment of hypothermia, coagulation and acidosis, that synergistically leads to catastrophic outcomes if not rapidly addressed. Coagulopathy manifests early in trauma cases, often culminating in death within six hours of the onset of bleeding.¹³ Swift identification and rectification of coagulopathy, along with hemorrhage control, remain the cornerstone of treatment for these individuals.¹⁴⁻¹⁸

ROTEM and TEG studies typically adhere to a standardized testing temperature of 37°Celsius, regardless of the patient's core temperature.¹⁹ Whether the 37°C sample accurately represents the viscoelastic clotting properties of a hypothermic patient remains unanswered. Our hypothesis posits that warming the blood sample to 37°C may artificially normalize ROTEM and TEG values, thereby downplaying true coagulopathy in bleeding trauma patients. We postulate that ROTEMs and TEGs conducted at the true core body temperature of hypothermic patients more accurately reflect a patient's impairment in blood clotting, as evidenced by more severe coagulopathy than their 37°C counterparts.

The objective of this study is to establish a high-quality, multi-center, prospective observational study of hypothermic trauma patients requiring viscoelastic monitoring. This study will compare viscoelastic tests conducted at the core temperature of hypothermic patients to their standard warmed samples. Our aim is to determine if ROTEM and TEGs conducted at a patient's core temperature provide better indications for resuscitation products and best practices for future hypothermic trauma patients. Data generated from this

prospective study will facilitate the exploration of various hypothesis-generating questions and may ultimately inform the development of new temperature specific algorithms. This initial study may guide efforts to secure funding for, and inform, randomized controlled trials evaluating patient outcomes when treated according to ROTEM or TEG samples run at patients' actual body temperature.

Several studies evaluating TEG and ROTEM show the benefit of viscoelastic guided resuscitation including: quick identification of patients at risk of bleeding, more precise and rapid reversal of coagulopathy, reduced mortality, decreased blood product administration, decreased ventilator days and shorter intensive care unit stays.^{17,20} Previous works evaluating these modalities in the hypothermic setting predominately utilize TEG as the test device; however, data is conflicting. Within these studies, researchers typically enrolled healthy individuals where samples are collected, cooled to test temperature and analyzed without warming. Cundrle et al. conducted a TEG study in patients requiring therapeutic hypothermia post cardiopulmonary resuscitation with minimal differences in in-vivo values at hypothermic vs. normothermic temperatures.²¹ Conversely, Forman et al. conducted TEG testing in encephalopathic neonates undergoing therapeutic hypothermia.²² They found TEG results differed significantly by temperature protocol with clinical risk for bleeding more frequently seen in the hypothermic assays. Additional studies have been conducted in hypothermic animals with varying levels of impact observed.^{23,24} There is limited data evaluating hypothermic ROTEM samples, and no large scale studies specifically evaluating viscoelastic monitoring at native temperatures in hypothermic trauma patients exist.

Briefly review what major published studies exist on the topic of the proposed project.

Local data: We conducted a pilot study at our institution evaluating the viscoelastic properties of ROTEM samples from hypothermic, bleeding trauma patients. We compared ROTEMs analyzed at patients' hypothermic core body temperature to standard 37°C samples obtained from the same patient. Twenty-four paired ROTEMs from 12 patients were analyzed. Median age was 48 (38-59), and 50% were male. The average temperature of hypothermic ROTEM assay was 34.2°C. Clot Formation Times (CFT) were prolonged within the hypothermic assay by an average of 45.4 seconds (EXTEM) and 51.3 seconds (INTEM), $p < 0.01$ for both (Figure 1). Maximum Clot Firmness (MCF) was decreased by an average 3.0 mm (EXTEM, $p = 0.01$) and 3.3 mm (INTEM, $p < 0.01$). EXTEM and INTEM A10 and A20 values additionally showed decreased amplitude using the hypothermic protocol (all $p < 0.01$). Using local ROTEM-directed transfusion guidelines, 25% of patients who did not meet platelet transfusion criteria based on standard protocol results, met transfusion criteria based on hypothermic protocol results.

Use this area to briefly outline how this idea is innovative and it's anticipated impact.

Data evaluating viscoelastic testing using hypothermic protocols is limited, with data predominately describing TEG use. Trauma patients in particular are at risk for coagulopathy from multiple etiologies, with early and efficient hemostatic resuscitation being one of the few interventions associated with positive mortality benefits. Expectedly, tests guiding transfusion and resuscitation need to be as accurate as possible. Our study is innovative because, other than our pilot study, this type of analysis has not been performed before. Our initial data is reassuring and indicates that statistically and clinically significant differences exist when comparing hypothermic assays to warm assays. Understanding the difference between hypothermic and warm assays is imperative to optimal resuscitation.

Describe what & how the proposed MCT will add to the existing body of knowledge & literature.

This MCT is needed to further quantify and expand upon our site's early data comparing hypothermic and standard ROTEM assay results. To date, no trials evaluating in-vivo hypothermic TEG or ROTEM assays exist in hypothermic trauma patients. Our aim is to fill the knowledge gap pertaining to the clinical impact of hypothermic testing, further identify and quantify blood product administration using hypothermic guided resuscitation practices, and ultimately compare hypothermic to standard protocols in a randomized controlled trial with intent to amend transfusion guidelines as indicated. Implementation and completion of this prospective multi-center trial is the first step towards these goals.

Determine if hypothermic testing protocols for ROTEM are associated with clinically significant differences in coagulation parameters compared to standard warm protocol testing. Our primary hypothesis is that results from hypothermic ROTEM assays will reflect more significant coagulopathy when compared to warmed samples. Our objective is to determine if hypothermic ROTEM samples will indicate a need for more plasma, cryoprecipitate and/or platelets for coagulopathy reversal compared to warmed samples.

Primary aim

To test the primary hypothesis, hypothermic ROTEMs parameters will be compared against standard warmed ROTEM samples. Two ROTEM samples will be drawn from each hypothermic trauma patient. The warmed 37°C sample will be compared to the sample analyzed at patients' core body temperature.

Secondary aims

Our secondary aim will be to evaluate if the coagulation parameter differences in hypothermic samples are replicated with TEG. Hypothermic TEG parameters will be compared against standard warmed TEG samples. Data for both TEG and ROTEM will be analyzed through our transfusion algorithm to determine if indicated blood products vary between hypothermic and warmed samples. We hypothesize that hypothermic TEG samples will demonstrate worse coagulopathy than warmed samples.

Tertiary aim

Determine if tranexamic acid (TXA) administration has an impact on fibrinolysis parameters in hypothermic patient samples. To assess TXA efficacy in hypothermic patients, a subset analysis in patients who receive TXA will be conducted. Hypothermic and standard assay results pertaining to fibrinolysis will be compared and will determine if a difference exists between samples.

Design

Prospective (observational with or without consent requirement)

Age: >18 years

Trauma patient

Core body temperature below 35C

Inclusion Criteria

Requires ROTEM or TEG testing as part of workup

Patients taking anticoagulants will be included as part of this study

Patients who are normothermic or hyperthermic at time of admission

Known pre-existing coagulopathy

Exclusion Criteria

Patients less than 18 years of age

Pregnant patients

Please describe, completely but succinctly, how the project will be conducted.

The Principal Investigator will carefully monitor study procedures to protect the quality of the data and the integrity of the study. This will be a prospective multi-center observational study of trauma patients evaluated in the emergency department. Blood samples collected for routine ROTEM and TEG testing will use excess blood to run a secondary sample at the reported hypothermic patient temperature. To do this block (ROTEM) or cup (TEG) heaters will be used in the standard fashion for the 37° Celsius sample; the second block or cup will be analyzed at the patients core body temperature. In addition to general viscoelastic monitoring results, we will also be accessing patient records for information regarding injury pattern, clinical parameters on ED admission, comorbid medical conditions, treatment, and outcomes.

Primary Outcome

Primary outcome: Numeric difference in hypothermic vs. warmed ROTEM and TEG samples.

Secondary Outcome(s)

Secondary Outcome: Theoretical difference in indicated blood products based on hypothermic vs. warmed assay results for both TEG and ROTEM samples.

Select the variables to be collected & analyzed:

Baseline Participating Institution Information, Demographics, Baseline Clinical Characteristics, Hospital Course, Treatments & Interventions, Outcomes of Interest

Additional variables:

Full data collection below

All data collected will be stored in REDCap and de-identified prior to sharing with research team members or participating sites. REDCap-stored data will include and be categorized in the following manner: demographics, patient clinical background, pre-intake data, laboratory data, admission clinical or hemodynamic data, TEG- or ROTEM-indicated intervention, post-admission interventions used, and patient outcomes.

Demographics: age, gender, weight, height, ethnic group, race, blood type, anticoagulant usage

Transfer data as applicable: EMS/flight transfer time, blood product and pre-hospital interventions

Laboratory data: hematocrit, hemoglobin, lactate, platelet count, base deficit, fibrinogen, INR, PT, PTT, thromboelastography (TEG) or (rapid TEG) or ROTEM

oTEG, rTEG, ROTEM data to include hypothermic data and standard protocol data

Outline the data collection plan/tool succinctly

Admission clinical or hemodynamic measures: Glasgow Coma Scale, systolic BP, mean arterial pressure, heart rate, respiratory rate, tissue oxygen saturation, arterial saturation, temperature, mechanism of injury, Injury Severity Score (ISS) and Abbreviated Injury Score (AIS) information when applicable, Arterial pH, Lactate

Blood product or hemostatic adjuncts administered: RBC, plasma, platelet, cryoprecipitate, tranexamic acid, aminocaproic acid, recombinant activated factor VII, fibrinogen, prothrombin complex concentrates

oIncludes field, referring hospital, inter-hospital transport, tertiary hospital, trauma bay, OR, and ICU product utilization

Patient outcome data: 28 day mortality and cause of mortality, ICU LOS, ventilator days, hospital LOS, total blood product utilization

oCause of death will be categorized into hemorrhage, CNS injury, multiple organ failure, or other

Has IRB approval been obtained at the primary site? Yes

Is DUA required for participation in the study? Yes

If applicable, list the primary contact (name/email) to contact to initiate & execute DUA: [name] - [contact]

Identify the individuals that will primarily be responsible for data collection process: All HIPAA compliant IRB approved personnel are eligible to assist with data collection to include: medical students, research team members, residents, fellows, and PIs

Is there a primary statistician assigned to assist the PI w/design & data analysis? Yes

If no, how was study design/power analysis determined/who will handle analysis once complete?

Effects of Interest. This is a single group study design intended to evaluate the potential need for modifications to current standard of viscoelastic monitoring in trauma patients. This study is strictly observational and no changes will be made to a patient's care as part of this study. The overarching research question: Should transfusion and resuscitation protocols that depend on viscoelastic monitoring parameters be modified to account for the coagulation metrics of hypothermic blood? To answer this, we must first identify whether treatment indications are dependent on the temperature of the blood sample being analyzed.

The primary effect of interest: Is there a statistical difference in coagulation metrics between hypothermic blood compared to warmed (current standard of care) blood in trauma patients? If so, what is the magnitude of difference between these testing methodologies?

The secondary effect of interest: Is there a statistical difference between hypothermic and standard viscoelastic tests that translates to clinically relevant changes regarding coagulopathy reversal? We plan to determine if using hypothermic TEG or ROTEM to guide resuscitation would result in a theoretically increased use of plasma, cryoprecipitate, platelets and TXA. To do this, we would determine the resuscitation strategy for each viscoelastic sample and – based on established transfusion thresholds – determine if hypothermic viscoelastic properties are different enough to result in a change in resuscitation approach (i.e., actual transfusion). Results of this study may inform future randomized controlled trials comparing the clinical effects of hypothermic patients treated with a resuscitation algorithm based on hypothermic ROTEM or TEG to those treated with standard ROTEM or TEG.

Include detailed description of the data analysis plan:

General Statistical Approach. Exploratory data analysis of all data collected will include the following overall summary measures for numerical variables: mean, standard deviation, minimum, maximum, and quartiles. For categorical data, we will construct frequency tables for each level within each variable. Bar charts, contingency tables, scatterplots and boxplots will be constructed to visualize associations as needed. Generalized linear models will be employed to evaluate relationships between variables, with random effect site (hospital), covariate effects for patient demographic and clinical characteristics, blood product and other intervention administration, TEG/ROTEM parameters by assay and temperature (hypothermic and warmed), and post-intervention clinical outcomes. Distributional, independence and homogeneity of variance assumptions will be investigated for each model evaluated and, if violated, transformations and/or nonparametric methods will be employed. Outliers will be identified

In a pilot study, we found that hypothermic samples, as compared to warmed samples, yielded effect sizes (mean difference divided by standard deviation of differences) from 0.94 to 1.85 for ROTEM parameters A10, A20, alpha and MCF for both the intrinsic and extrinsic assays. For a sample size of 15 (paired) samples and Type I error rate of 0.05, an effect size of 0.8 will provide 82.1% power to detect a significant difference between the paired samples (2-sided test).

Include Power Analysis:

In the same pilot study, ROTEM-indicated standard of care intervention protocol was as follows: warmed – Plasma: 3/12 = 25%, Cryoprecipitate: 6/12 = 50%, Platelets: 0 / 12 = 0%; hypothermic – Plasma: 2/12 = 16.7%, Cryoprecipitate: 6/12 = 50%, Platelets: 3/12 = 25%. In all, 5/12 = 41.7% had a different ROTEM-derived treatment indication based on the warmed sample compared to the results from the hypothermic sample. Given a trauma patient from this population with an assumed probability of needing a blood product treatment of 0.25, collecting 50 paired samples will provide 81.1% power to detect a 20% difference in treatment indications for a 2-sided test given $\alpha = 0.05$, based on a normal approximation to a paired 2-sample proportion testing design. To replicate this in both ROTEM and TEG and account for incomplete data entries, we aim to collect 150 paired samples (75 ROTEM and 75 TEG) for the study. We believe this would be possible to obtain with 7-10 ROTEM and 7-10 TEG sites (14-20 sites total).

Please note what your enrollment procedure for this study entails:

To permit a consecutive sample of patients at clinical sites and avoid sampling bias, we request a waiver of consent to collect data via medical record review. This study is minimal risk, observational, and involves no additional interventional procedures. Laboratory specimens collected as part of this study will be obtained as routine standard of care with small aliquots of excess blood used for hypothermic testing. Additional vials of blood are not required to conduct this study. Hypothermic results will not be entered into the patient chart or used to direct patient care. Discussion and study buy-in with laboratory personnel will be required as part of this study. Enrolled patients will have a ROTEM or TEG performed according to standard site protocol, and then an additional sample run at their hypothermic temperature.

Outline consent procedures here, if applicable:

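### The Significance section aims to show that core-temperature assays give better indications, but both outcomes measure only whether the two runs differ, so the study cannot show which run is right

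*Protocol*

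**What the plan says.** The protocol's Significance section makes two statements about validity. It postulates that assays at core temperature "more accurately reflect a patient's impairment in blood clotting, as evidenced by more severe coagulopathy than their 37°C counterparts". It then gives the purpose: "Our aim is to determine if ROTEM and TEGs conducted at a patient's core temperature provide better indications for resuscitation products".

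The outcomes are narrower. The primary one reads "Primary outcome: Numeric difference in hypothermic vs. warmed ROTEM and TEG samples". The secondary one reads "Theoretical difference in indicated blood products based on hypothermic vs. warmed assay results for both TEG and ROTEM samples". The Effects of Interest text asks whether the runs differ, by how much, and whether the difference would change the indicated products. It also says "we must first identify whether treatment indications are dependent on the temperature of the blood sample being analyzed".

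On conduct, the same text says "This study is strictly observational and no changes will be made to a patient's care as part of this study", and the enrollment section adds "Hypothermic results will not be entered into the patient chart or used to direct patient care". Clinical outcomes are collected: "Patient outcome data: 28 day mortality and cause of mortality, ICU LOS, ventilator days, hospital LOS, total blood product utilization". They are not named as study outcomes. They enter the analysis only through one general sentence on generalized linear models, which specifies no comparison of the two runs.

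**The concern.** Whether one test gives better indications than another is a question of validity. It needs something outside both tests to say when an indication was correct, and the protocol names nothing of that kind. The Significance section fills the gap by treating a worse reading as a truer one, which is circular. A cold run that merely shifts every value toward coagulopathy would meet that criterion whether or not it says anything about the patient's bleeding.

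What is at stake is the conclusion. The Background section itself says that undertreatment must be weighed against unnecessary exposure to blood products, so a false positive on the cold run is not harmless. A conclusion drawn by the Significance section's rule would count each extra cold indication as a gain in accuracy without evidence that it was one.

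**Working it through.** **1. The planned power concerns differences only.**
- Continuous parameters: 15 pairs, effect size 0.8, two-sided α = 0.05. A paired t-test with 14 degrees of freedom and non-centrality 0.8 × √15 gives 82.13%, against the stated 82.1%.
- Indications: 50 pairs, 25% against 45%. The McNemar normal approximation is Φ[(d√n − 1.96√p_disc)/√(p_disc − d²)], with d = 0.20. A within-pair correlation of 0.5 (my assumption; none is stated) gives p_disc = 0.26 and power of 81.25%, against the stated 81.1%.

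Both figures can be reproduced, and both are power to detect disagreement. Neither has an accuracy input.

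**2. The planned data cannot separate the two explanations.** Take 25% positive warm and 45% positive cold, and assume that all disagreement runs one way. The paired table is then 25% positive on both, 20% cold-only (10 of 50 pairs) and 55% negative on both.

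| If the true need is… | 37°C sensitivity | 37°C specificity | Cold sensitivity | Cold specificity |
|---|---|---|---|---|
| as the cold run reads | 0.25/0.45 = 55.6% | 100% | 100% | 100% |
| as the 37°C run reads | 100% | 100% | 100% | 0.55/0.75 = 73.3% |

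The table, and so the primary and secondary results, are the same in both rows.

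**3. The pilot does not move in one direction.** From the power section, warmed against hypothermic:
- platelets 0/12 against 3/12;
- plasma 3/12 against 2/12;
- cryoprecipitate 6/12 in both.

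At least one patient therefore lost a plasma indication on the cold run. By the protocol's own reasoning it is unclear whether that patient's cold result is more accurate or less. The net counts account for at most 3 + 1 = 4 changed patients, yet 5/12 changed. If the five refer to these three products only (an assumption), offsetting gains and losses are hidden in the plasma or cryoprecipitate totals.

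**4. Can the collected outcomes settle it?** One could take patients whose 37°C run does not indicate a product and compare outcome by cold result. That comparison misleads unless the 37°C value itself is in the model. Suppose the cold run is a constant shift of the 37°C value and carries no new information:
- the 37°C value X is standard normal (higher is worse), with 25% positive warm and 45% positive cold;
- outcome depends on X alone through a logistic model with an overall event rate of 30% (assumed).

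Averaging the event probability over X between the two cut-offs, and below the lower one, gives 33.2% against 22.6% for a log-odds slope of 0.5 per SD, and 34.9% against 16.5% for a slope of 1.0. Simulations with other inputs gave gaps from 9 points (29% against 20%) to 25 points (43% against 18%). The gap appears because cold-positive patients are those already near the 37°C threshold. Given X it is zero by construction.

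**5. Precision of such an analysis.** At the pilot platelet rate, 0.25 × 75 gives about 19 cold-positive and 56 cold-negative patients. The unadjusted 95% half-width is 1.96√[p(1−p)(1/n₁ + 1/n₀)].

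| Pairs | Groups | Assumed p = 10% | Assumed p = 30% |
|---|---|---|---|
| 75 | 19 vs 56 | 15.6 points | 23.8 points |
| 50 | 12.5 vs 37.5 | 19.2 points | 29.3 points |

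The second row matters because the 75 includes an allowance for incomplete data. The 25% rate is itself weak: the exact 95% interval for 3/12 is 5% to 57%.

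**The case against.** The strongest reply is that the sentence on better indications sits in a narrative section, while the operative parts are worded correctly. The primary aim compares parameters, the secondary aim asks whether indicated products vary, and the outcomes, Effects of Interest and power calculation agree with them. The greater-accuracy statement is a postulate, and the title says only that standard protocols may fail. The study is called initial and hypothesis-generating, and guideline change is tied to a later randomized trial. All of this stands, and it limits the point to the stated aim and the conclusion that may be drawn. It does not make that aim testable.

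A reader might go further and infer that every patient positive cold and negative at 37°C will be reported as missed coagulopathy, or that the study could by itself change transfusion algorithms. The protocol does not say so. It has no such reporting rule and labels these patients a theoretical difference in indication.

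It could also be said that outcome modelling belongs in the statistical analysis plan, which is not shown. That is fair, and its absence here is no fault. The wording of the aim and the accuracy argument, however, are fixed in this document.

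**Conclusion.** The point holds as a mismatch between the stated aim and the outcomes. The study can estimate how far the two runs differ and how often the indicated products change. It cannot show that the core-temperature run is more accurate. The illustration in step 2, with one-way disagreement assumed, shows the extent of what is left open: 55.6% sensitivity at 37°C and 73.3% specificity cold fit the same data.

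The paired comparison and its power are unaffected. The tempting idea that the collected outcomes could decide between the runs is not supported either. Care follows the 37°C result and not the cold one, so a head-to-head comparison against outcome is distorted by treatment. Restricting to 37°C-negative patients can still favour an uninformative shift (step 4), and the estimate would be imprecise (step 5). Those figures rest on assumed event rates, slopes and the pilot platelet rate.

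**What to change.** 1. In the Significance section, reword the aim as estimating the size of the temperature difference and the rate of reclassification of each indicated product, reported in both directions and not only as a net increase.
2. Delete the phrase that offers more severe coagulopathy as evidence of accuracy.
3. State that the study will not by itself conclude that core-temperature assays are more accurate, or that 37°C assays fail to identify coagulopathy.
4. Optionally, add an analysis labelled exploratory that relates the cold result to haemorrhage death and product use. The model should include the continuous 37°C value of the same parameter, ISS, base deficit and core temperature. Product use is itself treatment and should be read as such. The result should not serve as a gate for claiming that one run is better.

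Items 1 to 3 are text changes. Item 4 uses data already planned for collection. No patients or samples are added. The price is a more modest headline claim and, if item 4 is taken up, an imprecise estimate.

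### The tertiary TXA aim asks about an effect of TXA, but its recipients-only comparison of cold and 37°C assays cannot estimate one

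*Protocol*

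**What the plan says.** The Tertiary aim section of the protocol consists of three statements.

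- The question: "Determine if tranexamic acid (TXA) administration has an impact on fibrinolysis parameters in hypothermic patient samples".
- The population: "To assess TXA efficacy in hypothermic patients, a subset analysis in patients who receive TXA will be conducted".
- The contrast: "Hypothermic and standard assay results pertaining to fibrinolysis will be compared and will determine if a difference exists between samples".

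Four other places bear on it.

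- **Project conduct section**, on where the second assay comes from: "Blood samples collected for routine ROTEM and TEG testing will use excess blood to run a secondary sample at the reported hypothermic patient temperature".
- **Effects of Interest**, on the design: "This is a single group study design intended to evaluate the potential need for modifications to current standard of viscoelastic monitoring in trauma patients". The study is observational and does not assign TXA.
- **Data collection plan**: TXA is recorded among the hemostatic adjuncts, with coverage of "field, referring hospital, inter-hospital transport, tertiary hospital, trauma bay, OR, and ICU product utilization". Injury Severity Score (ISS), lactate and base deficit are also collected. Times of TXA administration and of the blood draw are not listed as fields.
- **General Statistical Approach**: generalized linear models are planned with "covariate effects for patient demographic and clinical characteristics, blood product and other intervention administration, TEG/ROTEM parameters by assay and temperature (hypothermic and warmed"). No TXA term, fibrinolysis outcome or TXA-by-temperature interaction is named.

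The Power Analysis covers the paired temperature contrast and the difference in treatment indications. It gives nothing for the tertiary aim.

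**The concern.** The question names TXA as the exposure, yet everyone in the analysis set has received it. The only factor that varies is the temperature at which the assay is run. No contrast between TXA and no TXA, or between samples before and after TXA, is specified for this aim.

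A null result would invite the reading that TXA has no impact in hypothermic patients, and a positive one that it has. Neither reading follows from the comparison. The protocol's own term, *efficacy*, encourages both. The Significance section hopes the data will inform temperature-specific algorithms and randomized trials, so a mislabelled result could be carried forward.

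**Working it through.** **Inputs.** The question, population and contrast come from the Tertiary aim section. The shared blood collection comes from the project conduct section. The documents give no number of TXA recipients and no mean, SD or effect size for any fibrinolysis parameter, so every magnitude below is assumed.

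**The protocol's own figure.** The Power Analysis states 82.1% power for 15 pairs at effect size 0.8, two-sided 5%. The noncentral t calculation gives 82.13%, so the figure reproduces. It concerns the temperature contrast and does not bear on the TXA question.

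**Step 1: what the planned contrast estimates.** Let X = 1 for a TXA recipient and 0 otherwise, and let u be the patient's own level. Let bX be the TXA effect, bT the effect of running the assay cold, and bI the TXA-by-temperature interaction.

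- Warm assay: Y(warm) = u + bX·X + e′
- Cold assay: Y(cold) = u + bX·X + bT + bI·X + e

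Among recipients (X = 1):

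E[Y(cold) − Y(warm)] = (bX + bT + bI) − bX = **bT + bI**

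The TXA effect bX drops out. Among non-recipients (X = 0) the same difference has expectation bT. Subtracting the second from the first gives (bT + bI) − bT = bI. The interaction is therefore identifiable only with non-recipients.

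**Step 2: a simple illustration (assumed values).** Suppose TXA halves lysis from 8% to 4% at both temperatures. The planned comparison is then 4% against 4%, a difference of 0. That is the right answer about temperature, and it says nothing about TXA.

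**Step 3: simulation.** Assumptions, none from the documents: 40 recipients and 40 non-recipients, between-patient SD 1, assay error SD 0.5, TXA exposure unconfounded, 1,500 replicates. Cells show the mean estimate and the share of runs with p < 0.05.

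| bT | bX | bI | Planned: cold − warm, recipients only | Recipients − non-recipients, cold assay | Difference in cold − warm between groups |
|---|---|---|---|---|---|
| 0 | 0 | 0 | 0.000 (5.5%) | 0.001 (4.1%) | −0.005 (4.6%) |
| 0 | −1 | 0 | −0.006 (5.4%) | −1.009 (98.4%) | −0.007 (5.3%) |
| 0.5 | 0 | 0 | 0.498 (98.9%) | 0.003 (5.1%) | 0.002 (4.9%) |
| 0.5 | −1 | 0 | 0.499 (98.7%) | −1.001 (98.0%) | 0.003 (4.5%) |
| 0.5 | −1 | 0.5 | 0.997 (100%) | −0.489 (48.3%) | 0.498 (88.1%) |
| 0.5 | 0 | −0.5 | 0.002 (5.0%) | −0.503 (51.9%) | −0.500 (87.0%) |

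Rows 1 and 2, and rows 3 and 4, differ only in whether TXA has an effect; the planned column does not change beyond simulation noise. Rows 1 and 6 give the same planned result, although row 6 has both a temperature effect and an interaction that offsets it. The last column recovers bI in every row. The cold-assay comparison estimates bX + bI, which is why it sits near −0.5 in rows 5 and 6.

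**The case against.** The strongest defence reads the third sentence of the aim as its real content: do cold and 37°C assays give different fibrinolysis readings in TXA-treated patients? That question is coherent, fits the rest of the protocol, and is answered by the planned comparison. This stands, and it is why rewording alone is an adequate repair. It does not rescue the text as written, because the first two sentences ask about the impact and efficacy of TXA. If the aim is instead taken to mean that TXA works differently in cold blood, that is the interaction, which still needs non-recipients.

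A second defence is that the general models already include intervention administration as a covariate. They do, so the plan as a whole is not confined to recipients. But that wording is generic, while the Tertiary aim section fixes its own analysis explicitly. Nor is this detail that can be left to a SAP: one that follows the section inherits the mismatch, and one that repairs it departs from the protocol.

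Third, the aim is tertiary and unpowered, and fibrinolysis appears in neither the primary nor the secondary outcome. That is correct and limits the severity.

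Three stronger readings are tempting but not supported.

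- **That the contrast measures temperature alone.** It also contains any TXA-by-temperature interaction.
- **That patients first given TXA after the draw will be in the subset.** The section sets no exposure window. The list running through OR and ICU says where product use is recorded and does not define the subset. The list also covers the field and transport, so some earlier exposure can be identified. The window is open, and no share of late recipients can be stated.
- **That the result will be published as TXA efficacy.** The protocol uses the word, but how the result will be reported is a prediction.

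**Conclusion.** The point holds as a mismatch between the tertiary question and its stated analysis. The cancellation of the TXA effect is algebraic. It requires only that both assays in a pair carry the same TXA exposure, which the use of excess blood from one collection ensures. The simulation values are illustrative and say nothing about the likely size of any effect in this study. Severity is minor to moderate.

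**What to change.** Choose one of two routes.

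**Route A, rewording.** Restate the aim as assay-temperature differences in fibrinolysis parameters among TXA recipients, and remove *efficacy* and *impact*. The planned analysis then matches its question. The cost is an edit to one paragraph, and the study makes no statement about TXA itself.

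**Route B, keep the TXA question.**

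1. Use all enrolled patients, and define exposure as TXA given before the index blood draw, with later first doses counted as unexposed.
2. Compare the within-patient cold-minus-warm difference between exposed and unexposed patients, which is the TXA-by-temperature interaction. Fix the measurement scale in advance, since an interaction depends on it.
3. Report exposed against unexposed at each assay temperature, adjusted for ISS and lactate or base deficit.
4. Call the result an exploratory association.

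Route B needs no extra patients or blood, and TXA use and the adjustment variables are already collected. TXA and draw times would have to be abstracted from the records at the planned 14 to 20 sites. Confounding by indication would remain, and admission lactate may itself follow pre-hospital TXA. Power is unknown: the number of recipients is not given, and the target of 75 ROTEM and 75 TEG pairs would be split by exposure within each device.

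Under either route, state the exposure window. Limiting it to TXA given before the draw ensures that patients counted as exposed had received the drug when they were sampled.
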